9.2. Selection of Sample Size

A maximum of 187 eligible subjects in Phase 1 and Phase 2 will be included in this study.

9.2.1. Sample Size for Phase 1

The primary objective of the dose escalation part in Phase 1 of the study is to determine the MTD or PAD of NC318. A 3 + 3 study design will be used for dose escalation. A maximum of 7 dose levels will be tested. Therefore, a maximum of 42 subjects, who are evaluable for DLTs, will be included in the dose escalation phase. Subjects evaluable for DLTs are defined as the subjects who take a full dose of NC318 and then are followed up for 28 days for assessment of DLTs. Any subjects who don't meet the criteria will be replaced.

Phase 1 of the study may also include safety expansion cohorts (Phase 1b) evaluating doses and schedules equivalent to or lower than the highest dose levels determined to be safe and/or doses determined to be pharmacologically active. Each safety expansion cohort will enroll a total of 9 evaluable subjects (up to 24 additional subjects). If < 3 of 9 evaluable subjects experience a DLT, the cohort will be deemed safe. If more than 1 safety expansion cohort is deemed safe, then the RP2D will be determined in conjunction with the investigators and sponsor based on all available safety, PK, PD, and biomarker results.

Phase 1 enrollment of the study is complete. A total of 49 subjects were enrolled across Phase 1a and Phase 1b. The following cohorts were expanded during Phase 1b: Cohort 2 (80 mg), Cohort 3 (240 mg), and Cohort 4 (400 mg).

9.2.2. Sample Size for Phase 2

Phase 2 of the study will further evaluate the safety, tolerability, preliminary efficacy, PK, and pharmacologic activity of the recommended dose of NC318. In Phase 2, subjects will be stratified after enrollment into cohorts based on S15 expression and tumor type.

9.2.2.1. Cohort 1: Select S15+ Tumors (Lung (adenocarcinoma), HNSCC, and Breast)

This cohort will include subjects who are 1) confirmed as TMB-H and/or MSI-H/dMMR, 2) upon enrollment are confirmed to express S15, and 3) have one of the following tumor types, separated into tumor-specific subgroup: 1a) Lung (adenocarcinoma), 1b) HNSCC, and 1c) Breast cancer. The sample size of each subgroup will be guided by the Simon 2-stage design ([Simon 1989](#)). Let 5% be a clinically insignificant response rate for all tumor cohorts. During Stage 1, each tumor-specific subgroup will enroll 9 evaluable subjects; if no responses are observed within a sub-group, then the sub-group will be discontinued. If 1 or more response is observed within a sub-group, then Stage 2 will begin and 8 additional subjects will be enrolled, for a maximum of

17 subjects within the sub-group. Each tumor-specific sub-group (1a, 1b, and 1c) will be independently assessed.

9.2.2.2. Cohort 2: Alternate Tumors (Other S15+ Tumors/S15- Tumors)

This basket cohort will include all other enrolled subjects who are confirmed as TMB-H and/or MSI-H/dMMR but do not fall under the criteria to be included in Cohort 1. Based on the result of S15 expression, subjects will be stratified after enrollment into two groups within the cohort: 2a) Other S15+ Tumors and 2b) Select 15- Tumors. Each group in the cohort will be guided by the Simon 2-stage design ([Simon 1989](#)). Let 5% be a clinically insignificant response rate for all tumor types. During Stage 1, 9 subjects will be enrolled into each group; if no response is observed within a group, then the group will be discontinued. If 1 or more responses is observed within a group, then Stage 2 will begin and 8 additional subjects will be enrolled, for a maximum of 17 subjects per group. Each group (2a and 2b) will be assessed independently.

9.3. Level of Significance

There is no formal hypothesis test planned for this study. A statistically significant level of 0.05 is used for calculation of CI.

9.4. Interim Analysis

No formal interim analysis is planned. However, the safety, PK and efficacy data will be regularly reviewed and monitored for deciding on dose escalation in Phase 1 and continuation in Phase 2 of the study.

9.5. Statistical Analyses

9.5.1. Summary of Baseline Characteristics, Demographics and Other Analyses

The number and percentage of subjects screened, treated, and the primary reason for discontinuation will be displayed. Demographic variables (e.g., age, gender), baseline characteristics, cancer history and diagnosis, and prior and concomitant therapies will be summarized either by descriptive statistics or categorical tables.

9.5.2. Safety Analyses

The safety assessments include adverse events, laboratory tests, and vital signs. All the safety data in the SAS will be summarized and listed by phase, treatment group, and cohort. Count and percentage of AE will be provided.

9.5.2.1. Adverse Events

A treatment-emergent adverse event (TEAE) is any AE either reported for the first time or worsening of a pre-existing event after the first dose of study drug. Analysis of AEs will be limited to TEAEs, but data listings will include all AEs regardless of their timing to study drug administration. Adverse events will be tabulated by the MedDRA preferred term and system organ class. Severity of AEs will be based on the NCI CTCAE v5.0 using Grades 1 through 4.

The subset of AEs considered by the investigator to have a relationship to study drug will be considered to be treatment-related AEs. If the investigator does not specify the relationship of the AE to study drug, then the AE will be considered treatment-related. The incidence, frequency, duration, and severity of all AEs (regardless of causality) will be tabulated.

9.5.3. PK Analyses

The PK analyses will be based off the PAS, and PK time-concentration data will be summarized, listed, and plotted. PK parameters (AUC_{0-336} , $AUC_{0-\infty}$, C_{max} , $t_{1/2}$, etc.) derived from time-concentration data will be summarized.

9.5.4. Efficacy Analyses

The response will be assessed by CT/MRI image during screening and every 8 weeks (\pm 7 days) post-dosing for 6 months and then every 12 weeks (\pm 7 days) thereafter (or per standard of care). The efficacy study endpoints include ORR, DCR, DoR, PFS, and OS. Tumor response will be determined according to RECIST v1.1. Time-to-event data (DoR, PFS, and OS) will be analyzed using the Kaplan-Meier method. All the efficacy data will be summarized by phase, dose group, and cohort.

- ORR includes RECIST v1.1 complete and partial response (CR or PR). ORR with 95% exact CI will be summarized by phase, dose group, and cohort.
- DCR includes RECIST v1.1 complete, partial response, and stable disease (CR, PR or stable disease). DCR with 95% exact CI will be summarized by phase, dose group, and cohort.
- DoR is defined as the duration from the first documented ORR to the first documented progressive disease or death due to any cause, whichever occurs first. For subjects who are alive and progression-free at the time of discontinuation from study, data cutoff for analysis, or use of other anti-cancer drug, DoR will be censored at the last tumor assessment date.

The DoR will only be analyzed for the subgroup of subjects with an objective response.

DoR = (progressive disease, death, or censored date) – (date of first response + 1)

- PFS is defined as from starting study treatment to the first documented progressive disease or death due to any cause, whichever occurs first. For subjects who are alive and progression-free at the time of discontinuation from study, data cutoff for analysis, or use of other anti-cancer drug, DOR will be censored at the last tumor assessment date.

PFS = (progressive disease, death, or censored date) – (date of first dose of study drug + 1)

- OS is defined as from starting study treatment to death due to any cause. For subjects who are alive at the time of discontinuation from study or data cutoff for analysis, OS will be censored at the date of last known alive (LKA).

OS = (Death or LKA date) – (date of first dose of study drug + 1)

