7.4. Poststudy Anticancer Therapy

The investigator or qualified designee will review all new anticancer therapy initiated after the last dose of study drug, including but not limited to systemic therapy, radiotherapy, and surgery.

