7.6.1.3. Tumor Imaging During the Study

The first imaging assessment should be performed 8 weeks after the first dose of study drug and then every 8 weeks (56 days \pm 7 days) for 6 months and then every 12 weeks (84 days \pm 7 days) thereafter until disease progression is determined. Imaging assessments may be done more frequently if clinically indicated. After completing 12 months of treatment, subjects will have imaging performed per standard of care and PI discretion. **Imaging should not be delayed for delays in cycle starts.**

Per mRECIST v1.1, response should be confirmed by a repeat radiographic assessment not less than 4 weeks from the date that the response was first documented. The scan for confirmation of response may be performed at the earliest 4 weeks after the first indication of response or at the next scheduled scan, whichever is clinically indicated.

Imaging should continue to be performed until documented disease progression, the start of new anticancer treatment, withdrawal of consent, death, or the end of the study, whichever occurs first. Disease progression should be confirmed at least 4 weeks, but no later than 6 weeks after the first scan indicating progression in clinically stable subjects. Subjects who have unconfirmed disease progression may continue on treatment until progression is confirmed, provided that they have met the conditions detailed in [Section 7.6.1](#). A central imaging vendor will not be used in this study.

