7.6.1.4. Imaging During Follow-Up

If the subject discontinues study drug for reasons other than disease progression, imaging assessments should continue at the Protocol-specified interval until documented disease progression, the start of new anticancer treatment, withdrawal of consent, death, or the end of the study, whichever occurs first.

If scan was obtained within 4 weeks prior to the date of discontinuation, then a scan at treatment discontinuation (EOT) is not mandatory. For subjects who discontinue study therapy without confirmed disease progression, a radiologic evaluation should be repeated at the time of treatment discontinuation (i.e., date of discontinuation \pm 4-week window). For subjects who discontinue treatment for reasons other than disease progression, every effort should be made to continue monitoring their disease status until 1) withdrawal of consent 2) the start of new anti-cancer therapy, 3) documented disease progression, 4) death, or 5) the end of the study, whichever occurs first.

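### The new-treatment censoring trigger for DoR and PFS covers drugs only, while scanning also stops at surgery or radiotherapy, so a death after an unscanned interval can count as the event

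*Combined protocol and SAP*

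**What the plan says.** On events, Section 9.5.4 states: "PFS is defined as from starting study treatment to the first documented progressive disease or death due to any cause, whichever occurs first". DoR runs from first documented response to the same two events. For subjects alive and progression-free, both bullets give three censoring triggers: leaving the study, the data cutoff, and another anticancer drug. The DoR bullet ends "data cutoff for analysis, or use of other anti-cancer drug, DoR will be censored at the last tumor assessment date". The PFS bullet carries the same sentence but also names DOR as the quantity to be censored. No rule covers progression or death after missed scans.

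Scanning ends on a wider trigger. Section 7.6.1.3 says: "Imaging should continue to be performed until documented disease progression, the start of new anticancer treatment". For subjects who stop NC318 without progression, Section 7.6.1.4 says that "imaging assessments should continue at the Protocol-specified interval until documented disease progression, the start of new anticancer treatment". Section 6.4.1 and footnote b of Table 7 agree. Section 7.4 has the site review "all new anticancer therapy initiated after the last dose of study drug, including but not limited to systemic therapy, radiotherapy, and surgery". Under Section 6.4.2 a subject who starts new anticancer therapy moves into Survival Follow-up, so the date of death is still recorded.

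Three other provisions bear on the point:

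- Section 5.6.3, in a list for the screening and treatment periods, counts palliative radiotherapy as clinical progression for PFS. It also says that subjects who need a listed therapy should leave the study.
- Section 5.5.1 says that stopping treatment is not withdrawal from the study.
- Section 5.5.2 says that a subject who permanently stops the drug is withdrawn from it.

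**The concern.** The plan accepts that a new treatment ends the period in which progression can be attributed to NC318, but Section 9.5.4 applies this to drugs only. The scan schedule applies it to every kind of treatment. A subject treated by surgery or radiotherapy alone falls between the two rules: nobody looks for progression any more, yet the subject stays at risk until death, which counts whatever its cause. The interval after the switch is then reported as progression-free or response time on NC318.

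The stake is mainly DoR, a named secondary objective (Section 2.1.2). A responder with limited residual disease is a plausible candidate for consolidative local treatment, and very few subjects may carry the DoR curve.

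**Working it through.** The documents state no median, event count or power for PFS or DoR, so there is no plan figure to reproduce.

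**1. The rules side by side.** Each row is a subject still on study who has the treatment before documented progression, takes no later anticancer drug (except in the first row), and dies.

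| New treatment | Scanning | PFS | DoR |
|---|---|---|---|
| Another anticancer drug | stops | censored at last scan | censored at last scan |
| Surgery alone | stops | event at death | event at death |
| Non-palliative radiotherapy alone | stops | event at death | event at death |
| Palliative radiotherapy alone | stops | progression at the radiotherapy (Section 5.6.3, not repeated in 9.5.4) | no rule, so event at death |

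**2. One responder (all dates assumed).** Weeks count from first dose. Partial response at week 16, drug stopped for toxicity with the last scan at week 24, resection at week 28, death at month 24 (about week 104). The one-day offset in the plan's formulas is ignored.

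- DoR as worded: 104 − 16 = 88 weeks, event.
- DoR censored at the last scan before the resection: 24 − 16 = 8 weeks.
- Interval without a scan: 104 − 24 = 80 weeks.
- PFS for the same subject: event at 104 weeks, or censored at 24.

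If this subject is alive at the data cutoff, or takes any anticancer drug before documented progression, the present text already censors DoR at 8 weeks. The 88 weeks arise only because the subject died.

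**3. Effect on a small DoR curve.** Section 1.3.4 reports 4 responders in 96 evaluable subjects. At that rate a subgroup of 17 would have 17 × 4/96 = 0.7 responders. The new subgroups are selected differently, so take three responders as an assumed case: the subject in step 2 and two others.

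- Others censored after week 88. As worded, the curve falls to 1 − 1/3 = 0.67 at week 88. With the wider trigger it stays at 1.0.
- Others progress, one after the other, between weeks 8 and 88 of response. As worded, the curve goes 2/3, 1/3, then 0 at week 88. With the wider trigger only two are at risk after week 8, and it goes 1/2, 0.

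The wider trigger raises the curve in the first case and lowers it in the second.

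**4. PFS simulation (all rates assumed).** 24 scenarios of 400,000 subjects, with:

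- median time to progression 2.5 or 5 months;
- median progression-to-death 3 or 8 months;
- median death without progression 60 months;
- 5%, 10% or 20% given local treatment before documented progression, unrelated to progression or within about 2 weeks before it, with no later drug;
- scans every 8 weeks, cutoff at 18 months.

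Truth means that scanning continues. Two scenarios for 6-month PFS:

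| Scenario | Truth | As worded | Wider trigger |
|---|---|---|---|
| Medians 2.5 and 8 months, 10%, unrelated | 0.202 | 0.239 | 0.212 |
| Medians 5 and 3 months, 20%, just before progression | 0.432 | 0.479 | 0.494 |

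Across all 24, the present wording exceeded the truth by about 0.010 to 0.085, and the wider trigger by about 0.005 to 0.062. The wider trigger was the higher of the two in 3 of 24. Medians agreed in every scenario but one (5.52 months truth, 6.06 as worded, 5.56 wider trigger). These runs concern PFS in very large samples and say nothing direct about DoR in a subgroup.

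**The case against.** The strongest reply is that other provisions already catch these subjects. Under Section 5.5.2 the subject in the example leaves the study when the drug stops, and the discontinuation trigger censors DoR at 8 weeks. Section 5.6.3 would likewise remove a subject who needs radiotherapy during treatment. This stands in part: the 88 weeks hold only on the reading in Section 5.5.1. But Sections 5.5.1 and 5.5.2 contradict each other. If 5.5.2 governed censoring, everyone who stops the drug would be censored, which would leave the follow-up imaging in Sections 6.4.1 and 7.6.1.4 without use for DoR and PFS. The list in Section 5.6.3 does not name surgery and is written for screening and treatment.

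Palliative radiotherapy is indeed a PFS event under Section 5.6.3, so PFS is not extended there. That answers one row of the table, and only for PFS.

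A reader might also infer that an end-of-treatment scan could fall after the switch and credit the other therapy's effect to NC318, because Section 7.6.1.4 says that "a radiologic evaluation should be repeated at the time of treatment discontinuation", with a 4-week window on either side. The documents do not support that as a separate defect. The imaging rule schedules no scan once new therapy has begun, and nothing says that the window overrides it. A clarifying phrase is enough.

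Finally, the stakes are limited. PFS and DoR are secondary and descriptive, Section 9.3 plans no formal test, and the Simon stage decisions use response only. Section 9 leaves further detail to the SAP, but nothing in the document reviewed supplies it here.

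**Conclusion.** The mismatch is in the text and should be corrected. It affects subjects who have non-drug treatment before documented progression, remain on study, take no later anticancer drug and die. Their individual times are inflated by the unscanned interval, by 80 weeks in the assumed example.

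A reader might infer that PFS and DoR are both overstated as estimates. The documents do not support that. They do not give the number of such subjects, those still alive are censored at the last scan under either rule, and turning an event into a censoring can raise a Kaplan-Meier curve. The simulated PFS excess rests wholly on assumed rates, and the median seldom moved. The case for acting is firmest for DoR, where one subject among very few responders can shape the curve. No error rate, sample size or stage decision is affected.

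**What to change.** In Section 9.5.4 and the SAP:

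1. In both bullets, replace the drug trigger with the start of any new anticancer therapy (systemic, radiotherapy or surgery, as in Section 7.4). Censor at the last tumor assessment on or before that start.
2. In the PFS bullet, name PFS, not DOR, as the quantity censored.
3. Carry the palliative-radiotherapy rule of Section 5.6.3 into the PFS bullet and state that it takes precedence over the censoring trigger. Otherwise the same radiotherapy would be both an event and a censoring. State how DoR handles it.
4. Reconcile Sections 5.5.1, 5.5.2 and 5.6.3 on what counts as discontinuation from study.
5. Report the present rule as a sensitivity analysis.

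The cost is a few phrases. Post-study therapy is already collected under Sections 6.4.1 and 7.4, and the sample size does not change. The downside is that a few observations become censored, possibly informatively, which is the reason for the sensitivity analysis.

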2.2.2. Secondary Endpoints

- 1) The endpoints for assessment of PK of NC318 include individual NC318 concentrations in serum and PK parameters.
- 2) The endpoints for assessment of antitumor activity/efficacy include objective response (OR) and DC based on RECIST v1.1, DoR, PFS, and overall survival (OS) as per RECIST v1.1
- 3) To evaluate expression of Siglec-15 in tumor tissue and immune cell infiltrates at baseline and following NC318 treatment, and correlate expression level with efficacy and changes in tumor infiltrating lymphocytes

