5.6.3. Prohibited Medications

Medications or vaccinations specifically prohibited in the exclusion criteria (see [Section 4.2](#)) are not allowed during the ongoing study. If there is a clinical indication for one of these medications or vaccinations specifically prohibited during the study, discontinuation from study drug may be required. The investigator should discuss any questions regarding this with the medical monitor. The final decision on any supportive therapy or vaccination rests with the investigator and/or the subject's primary physician. However, the decision to continue the subject on study drug or vaccination schedule requires the agreement of the investigator, the sponsor, and the subject.

Subjects are prohibited from receiving the following therapies during the screening and treatment periods of this study:

- Any anticancer medications, including chemotherapy or biologic therapy other than the study drug.
- Any immunological-based treatment for any reason from screening through safety follow-up visit.

Note: Completed adjuvant therapy (e.g., vaccines) with medical monitor approval.

Note: Inhaled or topical steroids and systemic steroids at doses ≤ 10 mg/day prednisone or equivalents are allowed.

Note: Immune suppressants are allowed for treatment of immune toxicities as described in [Section 5.4.7](#) and Brahmer et al. ([Brahmer 2018](#)).

Note: Allergy shots may be permitted after consultation with the medical monitor.

- Investigational agents other than the study drug from screening through the follow-up visits.
- Concomitant radiation therapy.

Note: Radiation therapy to a symptomatic solitary lesion or to the brain may be considered on an exceptional case-by-case basis after consultation with the medical monitor. The subject must have clear measurable disease outside the radiated field. Administration of palliative radiation therapy will be considered clinical progression for the purposes of determining PFS.

- Live vaccines within 30 days before the first dose of study drug *and* while participating in the study. Examples of live vaccines include, but are not limited to, the following: measles, mumps, rubella, chicken pox, yellow fever, rabies, *Bacillus Calmette–Guérin*, and typhoid (oral) vaccine. Seasonal influenza vaccines for injection are generally killed virus vaccines and are allowed. However, intranasal influenza vaccines (e.g., *FluMist*[®]) are live attenuated vaccines and are not allowed.

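### Section 5.6.3 makes palliative radiotherapy a PFS event, but the PFS definition and formula in Section 9.5.4 do not include it and do not refer to 5.6.3

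*Combined protocol and SAP*

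**What the plan says.** **Section 5.6.3 (Prohibited Medications).** Concomitant radiotherapy is prohibited, with an exception: "Radiation therapy to a symptomatic solitary lesion or to the brain may be considered on an exceptional case-by-case basis after consultation with the medical monitor". Measurable disease outside the irradiated field is a condition of the exception. The same note then gives an endpoint rule: "Administration of palliative radiation therapy will be considered clinical progression for the purposes of determining PFS".

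**Section 9.5.4 (Efficacy Analyses).** The definition reads: "PFS is defined as from starting study treatment to the first documented progressive disease or death due to any cause, whichever occurs first". The formula has three possible end dates: "PFS = (progressive disease, death, or censored date) – (date of first dose of study drug + 1". Response is tied to RECIST: "Tumor response will be determined according to RECIST v1.1". Censoring applies at discontinuation from study, at data cutoff, or on use of another anti-cancer drug. The DoR bullet ends that list with "use of other anti-cancer drug, DoR will be censored at the last tumor assessment date". The PFS bullet repeats the sentence and still names DOR rather than PFS as the quantity censored.

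**Section 2.2.2 (Secondary Endpoints).** PFS is listed in the phrase "DoR, PFS, and overall survival (OS) as per RECIST v1.1".

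Section 9.5.4 mentions neither clinical progression nor radiotherapy, and no other section reconciles the two rules.

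**The concern.** The sentence in 5.6.3 is an explicit instruction on how PFS is to be determined, so this is not a free choice between conventions. Someone programming PFS from 9.5.4 alone would not meet it. The same subject could be an event at the start of radiotherapy, still under observation, or censored at an earlier scan, depending on which section is followed.

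PFS will be reported by Kaplan-Meier for small cohorts. An irradiated subject who is not counted as an event pushes the curve upward. If the rule is settled only after the data are seen, the choice is open to the criticism that it followed the result.

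**Working it through.** The documents give no PFS rate, event count or power for PFS, so there is no figure of the plan's own to reproduce. The check is a comparison of text, followed by an illustration of scale.

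**1. One subject under each rule.** The subject receives palliative radiotherapy before any documented progression.

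- Section 5.6.3: event. The sentence gives no date; the natural one is the start of radiotherapy.
- Section 9.5.4, literal, subject stays on study: radiotherapy is neither documented progressive disease nor a drug. The subject stays at risk until RECIST progression, death or another censoring trigger.
- Section 9.5.4, radiotherapy read as other anti-cancer treatment: Section 7.4 lists anticancer therapy as "including but not limited to systemic therapy, radiotherapy, and surgery", though for therapy begun after the last dose. The subject is then censored at the last tumor assessment.
- Section 9.5.4, subject removed from study: the closing paragraph of 5.6.3 calls for removal of subjects who need the listed treatments. Discontinuation from study is a censoring trigger, so the result is again censoring.

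No reading of 9.5.4 on its own makes radiotherapy an event.

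**2. Shift for one subject.** The first scan is at week 8 and scans are 8-weekly for 6 months (Section 7.6.1.3).

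- Radiotherapy at week 7, RECIST progression at week 8: 7 versus 8 weeks, a shift of 1 week.
- Radiotherapy at week 4, first RECIST progression at week 16: 4 versus 16 weeks, a shift of 12 weeks.
- Radiotherapy at week 4, censored instead: the last assessment is the screening scan, so the subject contributes no follow-up.

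**3. Weight of one subject.** The maximum subgroup size is 17 (Sections 9.2.2.1 and 9.2.2.2), and 1/17 = 5.9%.

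**4. Illustrative simulation.** All inputs except n and the scan schedule are assumptions: n = 17; exponential PFS with median 8, 16 or 26 weeks; scans at weeks 8, 16 and 24, then 12-weekly; cutoff at week 52; 5%, 10% or 20% of subjects irradiated at a uniformly distributed time before the scan that shows progression; 1,500 replicates. The table gives the mean Kaplan-Meier PFS (%) just before the week-24 scan.

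| Median (wk) | Irradiated | Event (5.6.3) | At risk (9.5.4 literal) | Censored | At risk − event | Censored − event |
|---|---|---|---|---|---|---|
| 8 | 5% | 24.2 | 25.1 | 25.8 | 0.9 | 1.6 |
| 8 | 10% | 22.8 | 24.6 | 26.0 | 1.8 | 3.2 |
| 8 | 20% | 20.8 | 24.8 | 28.0 | 4.0 | 7.2 |
| 16 | 5% | 48.7 | 50.3 | 51.2 | 1.6 | 2.5 |
| 16 | 10% | 46.7 | 50.0 | 52.0 | 3.3 | 5.3 |
| 16 | 20% | 43.7 | 50.0 | 54.2 | 6.3 | 10.5 |
| 26 | 5% | 63.6 | 65.4 | 66.3 | 1.8 | 2.7 |
| 26 | 10% | 61.1 | 64.6 | 66.3 | 3.5 | 5.2 |
| 26 | 20% | 58.5 | 65.7 | 69.4 | 7.2 | 10.9 |

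Check on the at-risk column: a subject is event-free just before week 24 if true progression comes after week 16, so the expected value is 2^(−16/median). That gives 25.0%, 50.0% and 65.3%, in line with the table. Differences within a median in that column are simulation noise.

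**5. Scale against sampling error.** Near 50% with n = 17, 1.96 × √(0.5 × 0.5/17) = 0.238, or about ±24 percentage points. The rule matters less than chance, but it acts in one direction.

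**The case against.** The strongest reply is that 5.6.3 completes 9.5.4 rather than contradicts it. The definition in 9.5.4 speaks of documented progressive disease without naming RECIST in that sentence, and 5.6.3 gives a specific rule expressly for PFS. The RECIST phrase in 2.2.2 also covers OS, so it is loose wording. Section 9 leaves further detail to the SAP. On this view the defect is a missing cross-reference. That reading is possible, but nothing in 9.5.4 adopts it, and I found no further SAP text in the combined document that settles it. The repair is nearly the same either way.

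Four stronger readings are tempting, and the documents do not support them:

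- **That irradiated subjects will certainly be carried forward as progression-free.** This is one reading. Removal from study (5.6.3), or treating radiotherapy as anticancer therapy (7.4), leads to censoring.
- **That each affected event moves by at least one scan interval.** The week 7 versus week 8 case moves it by one week.
- **That the subgroup median will move.** With 17 uncensored times, the 9th ordered time changes only if the affected subject holds that position or crosses it. The irradiation rate is unknown, and 5.6.3 treats such radiotherapy as exceptional.
- **That DoR contains the same contradiction.** Section 5.6.3 names PFS only. DoR shares the event and censoring wording, so its handling should be stated, but no rule is breached.

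The requirement for measurable disease outside the irradiated field also means that progression can still be assessed after radiotherapy. This limits the loss of information but does not decide which date counts.

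**Conclusion.** The point holds. Section 5.6.3 gives a PFS rule that 9.5.4 neither contains nor cites. For the same subject the first gives an event, while the second gives continued follow-up or censoring. Both departures tend to lengthen PFS.

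The size cannot be derived from the documents. Under the assumptions above, week-24 PFS is about 1 to 7 percentage points higher if subjects stay at risk and about 2 to 11 points higher if they are censored. The upper ends need 20% of subjects to be irradiated, which fits poorly with an exceptional measure, so the practical effect is probably small.

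Consequences are limited. PFS is secondary, Section 9.3 plans no hypothesis test, and the stage decisions in 9.2.2 depend on responses. The correction is worth making because it costs little and fixes the rule in advance.

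**What to change.** In Section 9.5.4:

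1. Define the PFS event as the earliest of documented RECIST v1.1 progression, start of palliative radiotherapy (as 5.6.3 already states) or death from any cause. Refer to 5.6.3 and give the start date of radiotherapy as the event date.
2. Add a sensitivity analysis that counts only RECIST v1.1 progression or death, and say how irradiated subjects are followed or censored in it.
3. In the PFS bullet, replace DOR with PFS in the censoring sentence.
4. State how palliative radiotherapy is handled for DoR, as a matter of consistency.

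The exception in 5.6.3 and that section's closing paragraph on removal from study should also be reconciled by the sponsor, so that the analyst knows which irradiated subjects remain under observation. This review takes no position on that clinical rule.

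The cost is a change of wording and one extra Kaplan-Meier output. Sections 5.6 and 7.3 already require concomitant treatments and procedures to be recorded in the eCRF, so no new data item should be needed. The change should be made before database lock.
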